#### **2.5.3 Handling of missing values/censoring/discontinuations**

##### **CR analysis (safety run-in and expansion parts)**

For the determination of CR, only assessments after first dose of study treatment and prior start of any other anti-neoplastic therapy or HSCT are considered. An adequate response assessment is considered any disease assessment indicating response status apart from “unknown” or “not

done". Evaluation of response during study treatment relies on bone marrow and peripheral blood assessment, as well as on the presence or absence of extramedullary disease. A subject will be considered in complete remission if an adequate response assessment of CR is observed after first dose of study treatment and even if one or several inadequate response assessments ("unknown" or "not done") have been documented prior of CR determination.

#### **2.5.4 Sensitivity and Supportive analyses**

##### **CR analysis (safety run-in and expansion parts)**

The complete response (CR) rate with the exact 95% confidence interval will be presented for subjects assigned to the MBG453 400 mg Q4W dose level, as well as for all subjects from the FAS.

A listing of all derived efficacy endpoints by subject will also be provided including BOR, OS time, OS end date and duration of response. In addition, for some selected laboratory parameters and for bone marrow blasts percentage, trends over time (baseline and on-treatment timepoints during the first 12 cycles of treatment) will be displayed via boxplots and corresponding tables displaying the summary statistics for these selected timepoints be produced.

### **2.6 Analysis of secondary efficacy objective(s)**

Secondary efficacy endpoints will be analyzed and summarized for the FAS and by dose level of MBG453 (400 mg Q4W, 800 mg Q4W) and for all subjects ("All subjects" column), except those time-to-event endpoints (i.e., duration of response, EFS and OS).

The time-to-event endpoints will be analyzed and summarized for all subjects from FAS assigned to the MBG453 800 mg Q4W dose level only.

#### **2.6.1 Secondary endpoints**

Of note, all response assessments used for secondary efficacy endpoints/analyses will be based on investigators' assessments ([Cheson et al 2003](#), [Döhner et al 2017](#) and [Table 2-3](#)), unless otherwise stated.

#### **Duration of response**

The duration of complete remission (CR) will be assessed in subjects with best overall response of CR as per investigator assessment, defined as the time from achievement of CR as per investigator assessment (prior to any new antineoplastic therapy, including HSCT) to the first documented relapse from CR (including progression after CR) or death due to any cause, whichever occurs first. For subject without an event, duration of CR is censored at the date of last adequate response assessment.

Similarly, the duration of complete remission/complete remission with incomplete blood count recovery (CR/CRI) will be also assessed for subjects with best overall response of CR or CRI as per investigator assessment by considering the start date as the first documented CR or CRI (prior to any new antineoplastic therapy, including HSCT) whatever occurs first; and the duration of complete remission/complete remission with partial hematological recovery

(CR/CRh) will be assessed in subjects with best overall response of CR or CRh as per derivation ([Döhner et al 2022](#)) by considering the start date as the first achievement of CR or CRh (prior to any new antineoplastic therapy, including HSCT) whatever occurs first. Same censoring rule as duration of CR will be applied.

CRh will be assessed following the below criteria ([Döhner et al 2022](#)): neutrophil  $\geq 0.5 \times 10^9/L$  and platelets  $\geq 50 \times 10^9/L$  and otherwise all other CR criteria met. And note that all response categories and their occurrence dates used for derivation of duration of CR/CRh will be based on Novartis' derivation per [Döhner et al 2022](#). See [Appendix 5.2.2](#) for details.

The following events could occur after reaching response (CR, CRi or CRh) and may affect the interpretation of the results:

- Start of further anti-neoplastic therapy: For subject without an event before the time he/she receives any further anti-cancer therapy, duration of response would be censored at the date of the last adequate assessment prior to start of further anti-neoplastic therapy.
- Hematopoietic Stem cell transplantation (HSCT): For subject without an event before the time he/she receives an HSCT, duration of response would be censored at the date of the last adequate assessment prior to start an HSCT.
- Stopping study treatment (including due to toxicities): All events will be taken into account when they occur, regardless of any study treatment interruption or permanent discontinuation.
- Discontinuation from study due to lost to follow-up or withdrawal of consent: For subject without an event prior to discontinuation due to lost to follow-up or withdrawal of consent, duration of response will be censored at the last adequate assessment date.

The duration of response censoring reason will be summarized as:

1. Ongoing without event
2. New anti-neoplastic therapy
3. HSCT
4. Withdraw consent
5. Lost to follow-up
6. Discontinuation due to subject/physician/guardian's decision

### **Event-Free Survival (EFS)**

Event-free survival (EFS) is the time from date of start of treatment until date of death due to any cause, relapse from CR or CRi (including progression after CR or CRi), or treatment failure, whichever occurs first. Treatment failure is defined as lack of reaching CR until C8D1 or earlier permanent discontinuation from study without reaching CR (set to Day 1). As many cycles are delayed, the C8D1 time window for treatment failure is defined as the maximum of 7 cycles (including C8D1 assessment) or the first 7 months after start of treatment. A subject without EFS event will have their EFS censored at the time of the last adequate assessment performed on or before the cut-off date.

The following events could occur after start of treatment and may affect the interpretation of the results:

- Start of further anti-neoplastic therapy: For subject without an event before the time he/she receives any further anti-cancer therapy, EFS would be censored at the date of the last adequate assessment prior to start of further anti-neoplastic therapy.
- Hematopoietic Stem cell transplantation (HSCT): For subject without an event before the time he/she receives an HSCT, EFS would be censored at the date of the last adequate assessment prior to start an HSCT.
- Stopping study treatment (including due to toxicities): All events will be taken into account when they occur, regardless of any study treatment interruption or permanent discontinuation.
- Discontinuation from study due to lost to follow-up or withdrawal of consent: For subject without an event prior to discontinuation due to lost to follow-up or withdrawal of consent, EFS will be censored at the last adequate assessment date.

The EFS censoring reason will be summarized as:

1. Ongoing without event
2. New anti-neoplastic therapy

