3. HSCT
4. Withdrew consent
5. Lost to follow-up
6. Discontinuation due to subject/physician/guardian's decision

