### **2.6.2 Statistical hypothesis, model, and method of analysis**

No formal statistical tests will be performed for any of the secondary efficacy endpoints and hence no multiplicity adjustment will be applied.

Time-to-event endpoints will be analyzed using Kaplan-Meier method: the Kaplan-Meier curves, medians and 95% CI of the medians will be presented.

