### **2.6.3 Handling of missing values/censoring/discontinuations**

The censoring rules for time to event endpoints are described in the definitions above.

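### The EFS rules in SAP 2.6.1 conflict for a subject without CR who starts new therapy, unless Day 1 dating covers both failure limbs and takes precedence over censoring

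*SAP*

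**What the plan says.** SAP 2.6.1 (Event-Free Survival) ends EFS at death, "relapse from CR or CRi (including progression after CR or CRi), or treatment failure, whichever occurs first". It then defines failure by two limbs: "Treatment failure is defined as lack of reaching CR until C8D1 or earlier permanent discontinuation from study without reaching CR (set to Day 1". Since cycles often run late, it sets the length of the window as follows: "the C8D1 time window for treatment failure is defined as the maximum of 7 cycles (including C8D1 assessment) or the first 7 months", counted from the first dose.

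The section next lists things that may happen after start of treatment. For new therapy: "For subject without an event before the time he/she receives any further anti-cancer therapy, EFS would be censored", dated to the most recent adequate assessment beforehand. The transplant (HSCT) bullet is worded the same way. For loss or withdrawal: "For subject without an event prior to discontinuation due to lost to follow-up or withdrawal of consent, EFS will be censored", again dated to the most recent adequate assessment. The censoring reasons that follow include new therapy, HSCT, withdrawal, loss, and "Discontinuation due to subject/physician/guardian's decision". None of these is restricted to subjects who reached CR. SAP 2.6.3 adds no order of precedence; it says only: "The censoring rules for time to event endpoints are described in the definitions above".

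Protocol 12.5.1 has the same two failure limbs, but its second limb is permanent discontinuation with no mention of the study. It lists no EFS censoring for new therapy or HSCT. SAP section 4 declares no change to the protocol's analyses.

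**The concern.** A subject who never reaches CR is meant to be an EFS event. The censoring bullets, read as written, can apply to the same subject.

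The exposed case is the subject without CR who stops study treatment and starts another therapy before the C8D1 window closes, while still being followed for safety or survival. That subject has not left the study, so the SAP's second failure limb is not met. The first limb is settled only when the window closes, after the therapy has started. If the bullet is applied at that point, a non-responder becomes a censored observation.

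SAP 2.5.1 and 2.5.3 exclude any first CR after new therapy or HSCT. Taking that rule to carry over to EFS, this subject can no longer become a responder. The censoring would therefore be informative, with bias in one direction only: a more favourable EFS curve.

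**Working it through.** Neither document states an EFS figure, so there is none to reproduce. The check sets the rules side by side and then sizes the difference.

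**1. Scope of the bullets.** The duration-of-response bullets in SAP 2.6.1 are introduced as events after response has been reached. The parallel EFS bullets are introduced as events after start of treatment. The response condition is absent from EFS.

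**2. Does the second limb reach the switcher?** SAP 2.3.1 equates discontinuing the study with the end of survival follow-up. Protocol 9.1.1 says that stopping treatment is not withdrawal from the study. Protocol 9.1.1.1 continues safety follow-up for 150 days after the last MBG453 dose. With doses on schedule (Days 8, 36, 64), it runs to:
- last dose C1D8: 8 + 150 = Day 158
- last dose C2D8: 36 + 150 = Day 186
- last dose C3D8: 64 + 150 = Day 214

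An early switcher is therefore usually in safety follow-up, with survival follow-up to come, and is still in the study. The SAP's second limb is not met. The protocol's wording could be read to cover this subject.

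**3. When does the first limb close?** At the later of two times (28-day cycles; month length from SAP 5.1):
- 7 cycles: 7 × 28 = 196 days, so C8D1 is Day 197
- 7 months: 7 × 30.4375 = 213.06 days

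It closes no earlier than about Day 213. Under Protocol 9.1.1.2, post-treatment efficacy assessments end when new therapy starts.

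**4. Three readings of one case.** Assume no CR and new therapy on Day 91 (3 × 30.4375 = 91.3). With scheduled marrow assessments at C2D1 (Day 29) and C5D1 (4 × 28 + 1 = Day 113), the last one before therapy is Day 29.

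| Reading | Result |
|---|---|
| Day 1 covers both limbs; assigned dates are ordered at analysis | Event on Day 1 |
| Day 1 covers only the discontinuation limb | Failure not before about Day 213; new therapy comes first; censored at Day 29 |
| Day 1 covers both limbs, but the bullet is applied when therapy starts | No event recorded yet; censored at Day 29 |

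In both documents the Day 1 note follows the second limb, so the protocol does not settle which limbs it covers.

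**5. Size.** SAP section 1 gives 85 subjects treated at 800 mg, and SAP 2.6 limits time-to-event analyses to that dose. Let D be the number of Day 1 events when every non-CR subject is counted, and k the number censored later instead:

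KM just after Day 1 = 1 − (D − k)/85

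The rise is k/85, whatever the CR count. For one subject it is 1/85 = 1.18 points. The documents do not give k; for assumed values:

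| k (assumed) | Rise just after Day 1 |
|---|---|
| 1 | 1.2 points |
| 4 | 4/85 = 4.7 points |
| 8 | 8/85 = 9.4 points |

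**6. Direction.** Replacing a Day 1 event with later censoring removes one event and adds a subject to the risk set until the censoring date. Every Kaplan-Meier factor is equal or larger, so the curve cannot fall at any time.

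**The case against.** The best defence is that the dates already settle the order. EFS ends at whichever event comes first, failure is dated Day 1, and the new-therapy bullet applies only to a subject with no event before that therapy. A non-CR subject has an event on Day 1, so the bullet's condition is not met. The window's closing date shows when failure becomes known, not when it is dated. Windows should also be closed at analysis: the protocol's Amendment 5 reports all 90 subjects enrolled by 8 December 2022, and SAP section 1 puts the termination letter at 11 January 2024, 399 days later.

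Most of this stands, and it is the more natural reading. It depends on Day 1 covering both limbs, which the text leaves open. It also depends on a status fixed around Day 213 being placed ahead of a bullet triggered earlier, while the section's own bullet on stopping treatment counts events when they occur.

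A reader might infer that the SAP definitely censors non-responders, or that reported EFS will be biased. The documents do not support that: they permit the reading but do not require it. A reader might also give weight to the relapse wording, which is CR or CRi in SAP 2.6.1 but CR alone in Protocol 12.5.1 and SAP Table 1-1. That is a separate consistency note with almost no effect on the estimate.

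**Conclusion.** The point holds as a minor conflict between stated rules. The EFS text gives the intended result only if Day 1 dating applies to both failure limbs and takes precedence over censoring. Otherwise a subject without CR who switches therapy before the window closes is censored, and the curve rises by 1.2 points just after Day 1 for each such subject, with all other subjects handled alike.

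The size rests on the 85 subjects at 800 mg and on the rule that a CR after new therapy does not count. The number affected is unknown. No claim is made about the median, which depends on how many subjects reach CR by C8D1, also not given. HSCT without CR should be rare, because Protocol 5.1 excludes planned transplant.

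A reader might extend the concern to the trial's main conclusion. The documents do not support that: the primary CR analysis has its own rules, and for secondary efficacy endpoints SAP 2.6.2 states: "No formal statistical tests will be performed for any of the secondary efficacy endpoints".

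**What to change.** In the EFS part of SAP 2.6.1:

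- State that every subject without a qualifying CR by the end of the C8D1 window is a treatment failure dated Day 1. This includes subjects who, before then and without CR, stop treatment, withdraw, are lost, or start new therapy or HSCT. The event is the failure to reach CR, not the start of therapy.
- State that Day 1 applies to both limbs.
- Limit the censoring bullets and censoring reasons 2 to 6 to subjects who have reached CR.
- Reconcile the SAP's discontinuation *from study* with the protocol's unqualified wording, or record the departure in SAP section 4. Treat the CR versus CR/CRi relapse wording the same way.

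The cost is a few sentences and a small programming check, with no new data. If the program already orders by assigned date with Day 1 for both limbs, these precedence changes leave the results as they are. If not, EFS may look slightly less favourable.

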3. HSCT
4. Withdrew consent
5. Lost to follow-up
6. Discontinuation due to subject/physician/guardian's decision

## **Overall Survival (OS)**

OS is defined as the time from start date of treatment to date of death due to any cause. If a subject is not known to have died, then OS will be censored at the latest date the subject was known to be alive (on or before the cut-off date). All deaths will be taken into account whenever the death occurred, i.e. even after new anti-neoplastic therapy, HSCT, interruptions, or discontinuation of study treatment due to any reason.

## **CR/CRi rate**

CR/CRi rate is defined as the proportion of subjects with best overall response of either complete remission (CR) or complete remission with incomplete hematologic recovery (CRi) as per investigator assessment (see [Table 2-3](#)). CR/CRi rate will be provided with exact 95% confidence interval ([Clopper and Pearson 1934](#)).

## **CR/CRh rate**

CR/CRh rate is defined as the proportion of subjects with best overall response of either complete remission (CR) or complete remission with partial hematologic recovery (CRh) as per derivation ([Döhner et al 2022](#)). CR/CRh rate will be provided with exact 95% confidence interval ([Clopper and Pearson 1934](#)). Here, both CR and CRh will be based on Novartis' derived responses per [Döhner et al 2022](#). See [Appendix 5.2.2](#) for details.

## MRD negativity rate

MRD negativity rate is defined as the proportion of subjects with MRD negativity, which is defined as an MRD negative sample (frequency of LAIP below 0.1%, as determined by MFC-MRD at Central Lab) in subject with remission (bone marrow blast <5%, considering CR and/or CRI as per investigator assessment (see [Table 2-3](#)), and/or CR/CRh as per derivation ([Döhner et al 2022](#))). MRD-negative response should be observed at or after morphological remission, and prior to relapse or disease progression.

MRD data will be summarized descriptively at each scheduled timepoint post-baseline to assess number (%) of subjects with MRD-negative status.

MRD negativity rate by time points (incl. until Cycle 2 Day 1, until Cycle 5 Day 1, until Cycle 8 Day 1, and until Cycle 11 Day 1) and overall will be summarized descriptively with 95% exact confidence intervals ([Clopper and Pearson 1934](#)), in FAS, and in subgroups of interest (e.g., in subjects with overall response of CR/CRI as per investigator assessment (see [Table 2-3](#)), and CR/CRh as per derivation ([Döhner et al 2022](#)), and in subjects who are evaluable for MRD).

## Red blood cells (RBC)/Platelets transfusion independence

Red blood cells (RBC)/Platelets transfusion independence rate is defined as the proportion of subjects having received no RBC/Platelets transfusions during at least 8 consecutive weeks after start of treatment until end of treatment. The number and percentage of subjects will be shown for the overall FAS and then also in only those with transfusion dependence at baseline (i.e.  $\geq 1$  RBC or platelet transfusion in 8 consecutive weeks prior to start of treatment). Percentages will be provided with exact 95% confidence intervals ([Clopper and Pearson 1934](#)). Shift tables will be provided to describe the transfusion status at baseline versus the best transfusion status post-baseline. Transfusion status for RBC/platelets are defined as follows:

- Transfusion independence:
  - At baseline: subjects having received 0 units within the 8 consecutive weeks prior to baseline.
  - Post-baseline: subjects having received 0 units of transfusion within any 8 consecutive weeks during the study.
- Transfusion dependence:
  - At baseline: subjects having received  $\geq 1$  unit within the 8 consecutive weeks prior to baseline.
  - Post-baseline: subjects having received  $\geq 1$  unit of transfusion within any 8 consecutive weeks during the study.

Note, only AML-related transfusion would be counted. That is, transfusions for intercurrent disease or events not due to AML (e.g., bleeding due to trauma, surgical procedure) would not be taken into account.

For subjects with at least one period of transfusion independence post-baseline, the total duration of all transfusion independence periods will be also summarized. The duration of the transfusion independence is defined from the end date of the last transfusion received until the date transfusions are given again or last treatment in case transfusions had not (re-)started during

treatment. The total duration of all transfusion independence periods is the sum of each period of the transfusion independence.

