6.2 Other treatment(s)

6.2.1 Concomitant therapy

For participants enrolled all medications, procedures, and significant non-drug therapies/procedures (including physical therapy) taken within 28 days of starting study treatment until 150 days after the last dose of MBG453 or 30 days after the last dose of venetoclax or azacitidine (whichever was later) or until start of a new antineoplastic therapy must be recorded in the appropriate Case Report Forms. Concomitant medication administered to treat AE/SAEs suspected to be related to study treatment will continue to be collected up to the end of the safety follow-up period.

In general, the use of any concomitant medication/therapy deemed necessary for the care of the subject (e.g., such as anti-emetics, anti-diarrheal) is permitted (see [Section 6.2.1.1](#)), except when specifically prohibited (see [Section 6.2.2](#)). The subject must be told to notify the investigational site about any new medications he/she takes after the start of the study treatment.

Subjects should not receive pre-medication to prevent infusion reaction before the first infusion of MBG453. If a subject experiences an infusion reaction, he/she may receive pre-medication on subsequent dosing days. The pre-medication should be chosen per institutional standard of care, at the discretion of the treating physician.

Acute allergic reactions should be treated as needed per institutional standard of care. In the event of anaphylactic/anaphylactoid reactions, this includes any therapy necessary to restore normal cardiopulmonary status. If a subject experiences a Grade ≥ 3 anaphylactic/anaphylactoid reaction, the subject will be discontinued from the study treatment (see [Section 6.5.3](#) for guidance).

MBG453 should be administered in a facility equipped for cardiopulmonary resuscitation. Appropriate resuscitation equipment should be available, and a physician readily available.

Subjects should receive appropriate prophylaxis (e.g. antiemetics) for azacitidine as per local practice.

Blood transfusions received within 8 weeks before the first dose is administered, during the course of the study and until the end of post treatment follow-up, should be recorded in the appropriate Case Report Forms (see [Table 8-1](#)).

Intrathecal chemotherapy (e.g. cytarabine) administered as CNS prophylaxis, at time of diagnostic lumbar puncture, is permitted. All other use of chemotherapy is prohibited (see [Section 6.2.2](#)).

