- Transfusion dependence at baseline is defined as at least one RBC or platelet transfusion in the 8 weeks prior to C1D1

Extramedullary disease assessment

If clinical suspicion of extramedullary disease (EMD) exists or the subject has a clinical history of EMD, further evaluation using imaging assessments and other diagnostics (as clinically indicated) are required for subjects at screening. Presence or absence and physical location of EMD is to be captured in the CRF.

EMD is to be assessed via physical examination, cerebrospinal fluid (CSF) assessment in case of symptoms suggestive of meningeosis leukemia, and if clinically appropriate relevant imaging techniques.

In case of EMD at baseline or (re-) appearance during the study, the lesions should be considered for confirmation by imaging or biopsy if technically and/or clinically feasible. Imaging modalities and techniques should be performed as clinically indicated and per standard of care. Selected modalities should be used consistently for a given subject, if feasible.

If clinically indicated, post baseline imaging should only be performed in these anatomical regions that demonstrate possible disease.

EMD assessment, if applicable, will be performed at screening, C2D1 and every 3 cycles thereafter thereafter until confirmed CR, and then every 6 cycles thereafter until disease progression, start of a new anti-neoplastic treatment (including HSCT), death, lost to follow-up or withdrawal of consent.

Post-treatment efficacy follow-up

Subjects who discontinue treatment for reasons other than documented disease progression/relapse from CR, start of a new anti-neoplastic treatment (including HSCT), death, lost to follow-up, or withdrawal of consent, will enter the post-treatment follow-up phase ([Section 9.1.1.2](#)). Hematology assessments must continue to be performed every 3 months, response should be assessed at least every 6 months, and bone marrow assessment should be done at least every 3 months until CR and every 6 months thereafter per [Table 8-1](#), or as clinically indicated any time in case disease progression is suspected. Further information about blood transfusions will be continuously collected throughout the post treatment follow-up period.

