9.1.1.3 Survival Follow-up

Patients will enter the survival follow-up period once they complete the safety follow-up period or have disease progression (whichever is later). Patients will then be contacted by telephone every 12 weeks to follow-up on their survival status. Any new anti-neoplastic therapy that has been started since the last contact date (including HSCT) and any SAEs related to study treatment, as well as information about the remission status and the date of progression/relapse from CR for patients who receive a HSCT will also be collected during these phone calls.

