
 
To assess the CR/CRh rate and the duration of CR/CRh
 
	
 
Proportion of subjects achieving a CR or complete remission with partial hematologic recovery (CRh), as per derivation (Döhner et al 2022)
 
Time from the date of the first CR/CRh to the date of first relapse or progressive disease or death due to any cause, whichever occurs first, as per derivation (Döhner et al 2022)
 

 
To assess the Event-free Survival (EFS)
 
	
 
The time from start of treatment until date of death due to any cause, or relapse from CR, or treatment failure defined as failure to reach CR by Cycle 8 Day 1, whichever occurs first, as per investigator assessment (Cheson et al 2003, Döhner et al 2017)
 

 
To assess Overall Survival (OS)
 
	
 
The time from start of treatment to death due to any cause
 

 
To determine safety and tolerability of MBG453 when administered in combination with azacitidine and venetoclax
 
	
 
Incidence and severity of AEs and SAEs, changes in laboratory values and vital signs, incidence of notable ECG abnormalities
 

 
Characterize the pharmacokinetics (PK) of MBG453 when administered in combination with azacitidine and venetoclax
 
	
 
Pharmacokinetic parameters (serum concentrations for MBG453 and plasma concentrations for venetoclax)
 

 
To evaluate immunogenicity of MBG453 when given in combination of azacitidine and venetoclax
 
	
 
Anti-drug Antibody (ADA) prevalence at baseline and ADA incidence on-treatment
 

 
To assess the effect of MBG453 in combination of venetoclax + azacitidine on transfusion independence
 
	
 
Number and percent of all subjects who achieve transfusion independence on treatment, and from baseline respectively.
 

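### The SAP's shift tables judge transfusion independence over the whole study while the rate stops at end of treatment, and the duration rule lacks a proper start date

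*SAP*

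**What the plan says.** The secondary endpoint in SAP Table 1-1 is "Number and percent of all subjects who achieve transfusion independence on treatment, and from baseline respectively".

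SAP 2.6.1 (Red blood cells (RBC)/Platelets transfusion independence) then gives three rules:

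- **Rate.** The proportion of subjects free of transfusion "during at least 8 consecutive weeks after start of treatment until end of treatment".
- **Shift tables.** "Shift tables will be provided to describe the transfusion status at baseline versus the best transfusion status post-baseline". Post-baseline independence is "subjects having received 0 units of transfusion within any 8 consecutive weeks during the study". Post-baseline dependence uses the same study-wide window.
- **Duration.** For subjects with a post-baseline independence period, duration "is defined from the end date of the last transfusion received until the date transfusions are given again", or until last treatment if transfusions had not restarted during treatment. Protocol 12.5.1 has the same rule.

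On data collection, Protocol 6.2.1 says that transfusions from 8 weeks before the first dose, and "during the course of the study and until the end of post treatment follow-up, should be recorded in the appropriate Case Report Forms". The phase named there is entered by "Subjects who discontinue treatment for reasons other than documented disease progression/relapse from CR" and a few other listed reasons (Protocol 8.3.1). SAP 2.3.1 equates the end of study with the end of survival follow-up.

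**The concern.** The endpoint is independence on treatment, and the rate respects that. The shift-table status does not. Because best status is used, a single qualifying 8-week gap anywhere up to the end of survival follow-up makes a subject independent. That gap may fall after treatment has failed, after another therapy has begun, or where nobody was recording transfusions. Two tables for the same endpoint could then disagree about the same subjects, and always in the same direction: a wider window can only add independent subjects.

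The duration rule has a separate weakness. Its start is tied to a transfusion rather than to the start of treatment. That start can precede C1D1, or not exist at all for a subject with no recorded transfusion, who has the best possible outcome.

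**Working it through.** The documents give no expected rate, sample size or power for this endpoint, so there is no figure to reproduce. The check compares the definitions with the collection schedule and then applies the duration rule literally to assumed dates.

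**1. Windows**

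| Item | Window | Source |
|---|---|---|
| Endpoint | On treatment | SAP Table 1-1 |
| Rate | Start to end of treatment | SAP 2.6.1 |
| Shift-table status | Any 8 weeks in the study; best status | SAP 2.6.1 |
| End of study | End of survival follow-up | SAP 2.3.1 |

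The status rule has no cut-off at new therapy or HSCT. The CR rule in SAP 2.5.1 and 2.5.3 does have one.

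**2. Where recording stops**

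- Protocol 6.2.1 requires concomitant therapy to be recorded until 150 days after the last MBG453 dose or 30 days after the last venetoclax or azacitidine dose, whichever is later, or until new antineoplastic therapy. The corresponding row of Protocol Table 8-1 includes blood transfusions and is marked for safety follow-up. Protocol 9.1.1.1 applies safety follow-up to all patients.
- Subjects who enter post-treatment follow-up continue to have transfusions recorded there (Protocol 8.3.1 and Table 8-1).
- Survival follow-up calls (Protocol 9.1.1.3) collect survival status, "Any new anti-neoplastic therapy that has been started since the last contact date (including HSCT) and any SAEs related to study treatment", and remission information after HSCT. Transfusions are not listed.

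Take a subject who stops for progression, starts no new therapy, and has the MBG453 limit as the later one. A wholly unrecorded 8-week window is complete at 150 + 56 = 206 days after the last MBG453 dose. New therapy can bring that forward.

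**3. Duration rule on assumed dates (days from C1D1)**

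Literal formula: duration = (next transfusion, or last treatment if none) − end of last transfusion.

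- *A. Last transfusion 42 days before C1D1, none after, last treatment at day 168.* The literal result is 168 − (−42) = 210 days. Starting at C1D1 gives 168. The excess is 42/168 = 25%. Transfusions are collected from 56 days before first dose, so the credit ranges from 1 day (1/168 = 0.6%) to 56 days (56/168 = 33%). In months the maximum is 56/30.4375 = 1.84.
- *B. No recorded transfusion, last treatment at day 168.* The formula has no start date and returns nothing. Starting at C1D1 gives 168 days.
- *C. Transfusions at days −10, 20, 60, 95 and 110, last treatment at day 100, none recorded afterwards for at least 8 weeks.* The gaps up to day 110 are 30, 40, 35 and 15 days, all below 56. The rate table therefore says not independent. The gap after day 110 makes the subject independent in the shift table. The duration of that only qualifying period is 100 − 110 = −10 days.

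Case C needs no missing data. A recorded transfusion-free gap after treatment produces the same disagreement.

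**The case against.** The strongest reply is that little of importance is exposed. The reported rate, with its exact confidence interval, ends at end of treatment. The endpoint is secondary and descriptive, with no formal test (SAP 2.6.2), and no success criterion uses it. That stands, and it limits the weight of the point.

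A second reply is that a programmer would read the status in line with the rate beside it, and would start duration at C1D1, since the rule covers post-baseline periods and ends at last treatment. That may well happen, but the SAP does not say so. Protocol 8.3.1 also leaves the post-baseline window open-ended, which gives no help.

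A third is that stopping status at end of treatment sets aside post-treatment transfusion data that the protocol collects on purpose. That is fair. Such data can be shown separately, up to the last date of recording.

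A reader might infer more: that recording ceases as soon as a subject stops for progression, so that the shift tables would be inflated by many percentage points. The documents do not support this. Safety follow-up still captures transfusions, and neither the number of subjects lacking an 8-week on-treatment gap nor their survival beyond recording is given.

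**Conclusion.** The point holds as an internal inconsistency with a known direction and unknown size. Followed literally, the shift tables can class as independent subjects who are not independent in the rate table. This can happen through recorded off-treatment time or, later, through unrecorded time read as zero units. The second route opens only after safety follow-up collection ends and, for those who enter it, after post-treatment follow-up ends. No estimate of the number of subjects affected can be drawn from the documents.

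The duration faults follow directly from the wording: a pre-treatment credit of up to 56 days, no start date for a subject with no recorded transfusion, and possible negative values. The 210-day and −10-day results rest on assumed dates and only illustrate the rule.

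The damage is confined to the shift tables and the duration summary. It would be wrong to conclude that the main independence rate is biased, because its window is bounded.

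**What to change.** In SAP 2.6.1:

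1. In both post-baseline status definitions, replace the study-wide window with the interval from first dose to end of treatment, matching the rate. Class a subject with no transfusion-free 8-week window in that interval as not independent.
2. If post-treatment status is of interest, show it separately and stop it at the last date of transfusion recording for each subject.
3. Start each independence period at the later of C1D1 and the end date of the last transfusion. Use C1D1 if no transfusion is recorded.

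The cost is SAP wording and programming, with no new data. The shift table may look less favourable.
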